ΔCrepitus Ant. Compartment	none	moderate	mild pain	>mild pain				
ΔCrepitus Med. Compartment	none	moderate	mild pain	>mild pain				
ΔCrepitus Lat. Compartment	none	moderate	mild pain	>mild pain				
5. Harvest Site Pathology	none	mild	moderate	severe				
6. X-ray Findings								
Med. Joint Space	none	mild	moderate	severe				
Lat. Joint Space	none	mild	moderate	severe				
Patellofemoral	none	mild	moderate	severe				
Ant. Joint Space (sagittal)	none	mild	moderate	severe				
Post. Joint Space (sagittal)	none	mild	moderate	severe				
7. Functional Test								
One Leg Hop (% of opposite side)	≥90%	89 to 76%	75 to 50%	<50%				
**Final Evaluation								

G. Experimental Design

Patients will be randomized using a computer generated randomization table (simple randomization) into one of two treatment arms:

(1) Autologous BPTB ACL reconstruction followed by application of PRP soaked bone chips = Treatment

(2) Autologous BPTB ACL reconstruction = Control

The patient, research personnel and individuals collecting all objective outcome measures will be blinded to the randomization. The operating surgeons (SJM or BB) will evaluate the subjects pre and post operatively but will not contribute any of their objective data collection to the study. Randomization and patient assignments will be done through sequentially numbered opaque sealed envelopes by the circulating nurse in the OR at the time of surgery. The randomization will not be stratified according to surgeon but rather-according to treatment arm. Randomization information will then be recorded and placed into a sealed envelope with the patients' randomization ID and deposited into a locked reception box. This box will only be opened upon completion of the study.

H. Research Procedure

ACL reconstruction

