We plan to enroll approximately 100 patients with 50-treatment/50 controls. Power analysis was based upon previous studies examining kneeling pain using a VAS in patients undergoing ACL reconstruction with Autologous Bone Patellar Tendon Bone graft harvest. Feller et al (2001) reported kneeling pain to be 4.5+/-2.1 4 mo. after surgery, Wipfler et al (2011) reported kneeling pain to be 1.6+/-0.7 1 yr after surgery, and Siebold et al (2006) reported kneeling pain to be 4.0+/-3.1 3.8 yr after surgery (mean +/-SD reported). A 2-point difference in kneeling pain between groups would be regarded as clinically significant. The between subject SD for kneeling pain of averaged 2.0 for the 3 studies cited above with an upper limit of approximately 3.0. Therefore we conservatively based the sample size estimate to demonstrate a 2.0 difference in VAS pain between groups on a SD of 3.0. It is estimated that with 35 patients per group there will be 80% power to detect a 20% difference in kneeling pain (2 points on a 10 point scale) at an alpha level of 0.05. This estimate was calculated using the equation described by Kirkwood et al (1988).

Assuming a loss to follow up of up to 30% at two years, adequate sample recruitment was determined to be 50 per group or 100 total.

References Cited for Power Analysis

- 4:Kirkwood BR (1988). Calculation of required sample size. In *Essentials of Medical Statistics.* pp 191-200. Oxford. Blackwell Scientific Publications.

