L. Data Safety Monitoring Board: The data safety monitoring plan for this study will involve patient follow-ups and interim analysis. At each follow-up session, the investigator will assess healing of both the donating and recipient sites. If any infections are present, they will be addressed as per standard of care which involves cleaning the area arthroscopically. The investigator will also perform an interim analysis after half of the accrual goal is achieved. At this point, study data will be reviewed by the investigator to ensure patient safety and the continued validity of the study.

M. Potential Benefits:

The participants randomized to receive PRP in this study may directly benefit by having decreased healing time and decreased post operative pain, specifically anterior knee pain common to patients in the postoperative time frame following autologous BPTB reconstruction of their ACL. The study may provide knowledge on the benefits of PRP in graft site healing and patient satisfaction following ACL reconstruction.

N. Discontinuation of Study/Subject Withdrawal

A patient may be withdrawn from the study due to lack of follow up or voluntary withdrawal. The study may also be discontinued at any time depending on the circumstances and any adverse events on the discretion of the investigating personnel and the IRB.

O. Adverse Events

If the patient has any adverse effects from being in the study, they will receive medical care and treatment as needed from the North Shore-Long Island Jewish Health System. However, the patient will be responsible for the costs of such medical treatment, directly or through their medical insurance and/or other forms of medical coverage. No money will be given to the patient. All adverse events will be reported as necessary, per NSLIJ IRB policy.

P. Confidentiality

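### The half-accrual safety review in section L can use only pooled events, because section G keeps every recorded allocation sealed until the study is complete

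*Combined protocol and SAP*

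**What the plan says.** Section L (Data Safety Monitoring Board) bases safety monitoring on follow-up visits and one interim look. Both surgical sites are assessed at each visit, and infections are managed patient by patient. On the interim look it says: "The investigator will also perform an interim analysis after half of the accrual goal is achieved". Its purpose follows: "At this point, study data will be reviewed by the investigator to ensure patient safety and the continued validity of the study". The section does not say whether the review is pooled or by arm, and despite its heading it describes no independent board.

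Section G (Experimental Design) has the circulating nurse assign patients from numbered sealed envelopes. The assignment is then recorded, sealed again and put in a locked box: "This box will only be opened upon completion of the study". No exception is given for the interim review or for a patient with an adverse event. Patients, research personnel and outcome assessors are blinded.

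Three other passages bear on the point:
- Section N, where the IRB is the second party named: "The study may also be discontinued at any time depending on the circumstances and any adverse events on the discretion of the investigating personnel and". No criterion is given.
- Section O: adverse events go to the IRB under its policy. Arm is not mentioned.
- Section P: access to the data is limited to the investigators.

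**The concern.** The trial compares two procedures that differ only in the PRP. A review meant to protect patients from harm caused by PRP would ordinarily look at events by arm. If it cannot, an excess confined to the PRP group is diluted by the control group and mixed with the background risk of the operation.

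Infection is the harm that section L itself names. Under section H only the PRP arm has blood drawn, centrifuged and mixed with calcium chloride, and the bone chips soaked in the product until the end of the case. Half of the planned patients, about 25 of them assigned to PRP, are operated on after the only aggregate review.

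**Working it through.** **Timing of the review.** Section I states: "We plan to enroll approximately 100 patients with 50-treatment/50 controls". That total reproduces. The inputs are a 2-point difference, SD 3.0, alpha 0.05 (two-sided) and 80% power:

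n per group = 2 × [3.0 × (1.960 + 0.842) / 2.0]² = 35.3, against the stated 35.

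With 30% loss, 35 / 0.70 = 50 per group, or 100 in all. Half of accrual is therefore about 50 patients, about 25 per arm. About 50 remain, of whom about 25 would receive PRP.

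**What the review can see.** Section G seals the recorded allocation until completion, without exception. Section L takes place before completion and grants no access. Applying both exactly leaves one possibility: the review sees total events among about 50 patients, with no arm attached. Randomization is simple, so even the number treated per arm is unknown to a blinded reviewer. The SD is √(50 × 0.25) = 3.54, giving a 95% range of 25 ± 1.96 × 3.54, or about 18 to 32 on PRP.

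**What pooling hides.** With 25 per arm and no PRP effect, the chance that all k infections fall in the PRP arm is C(25,k) / C(50,k):
- k = 3: 2,300 / 19,600 = 11.7%
- k = 4: 12,650 / 230,300 = 5.5%
- k = 5: 53,130 / 2,118,760 = 2.5%

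A pooled count of four does not distinguish 2 v 2 from 4 v 0. If arm sizes are left to simple randomization, the k = 4 figure is 0.5⁴ = 6.25%.

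**What pooled and by-arm counts could show.** The documents give no infection rate, so every rate below is an assumption: 1% in controls, 25 patients per arm. Expected pooled events are 25 × (control rate + PRP rate). The cut of three events is for illustration only.

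| Assumed PRP rate | Expected pooled events in 50 | P(3 or more pooled) | P(one-sided Fisher p ≤ 0.05 if arms known) |
|---|---|---|---|
| 1% | 0.5 | 1.4% | – |
| 5% | 1.5 | 18.8% | 0.6% |
| 10% | 2.75 | 52.7% | 8.3% |
| 20% | 5.25 | 91.8% | 52.9% |

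The pooled count is informative only against a known background. If both arms had a 2% rate, three or more pooled events would occur with probability 7.8%, not 1.4%.

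If the arms were known, two-sided Fisher p-values would be 0.23 for 3 v 0, 0.11 for 4 v 0, 0.050 for 5 v 0 and 0.022 for 6 v 0.

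**The case against.** A reader might infer that an excess of infections on PRP can be neither seen nor acted on during the trial. The documents do not support that. Both sites are checked at every visit, section O sends adverse events to the IRB, and section N lets the investigating personnel and the IRB stop at any time. All of this continues after the half-way review. A high pooled count could lead to a stop without anyone knowing the arm and, if the background rate is low, would itself be a signal.

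A reader might also call sections L and G a flat contradiction. They are not: section L never says that its review is by arm, and a pooled review satisfies both. Nor is the arm hidden from everyone. The circulating nurse assigns it, and since only PRP patients are bled, the anesthesiologist and the operating-room assistant can infer it. The documents do not say who holds the randomization table.

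It is also fair to say that opening the arms would settle little at this size (4 v 0 gives p = 0.11). The documents also give no ground for expecting high infection rates: section K rates the risk of PRP as very low, section H describes a sterile, covered cup, and controls have bone chips placed too. The absence of a numerical trigger is a detail left to discretion and is not the point here.

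What stands is narrower. The staff who know the arm have no reporting role, the routes in sections L, N and O have no stated access to it, and section G's rule on the box closes the recorded allocation until the end.

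**Conclusion.** The point holds as a mismatch between the purpose of the section L review and the rule in section G. As written, the only planned aggregate review can use pooled events alone, and no stated route compares infections by arm during accrual. Action on a pooled count remains possible under section N.

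The size cannot be fixed from the documents, because they give no infection rate; the table is illustrative. What follows from the plan's own numbers is that about 50 patients are covered by the review and that about 25 receive PRP after it. By-arm counts of about 25 would be weak evidence taken alone. Their value is in telling those who use section N's discretion whether a cluster is shared or one-sided. The conclusion assumes that section G means what it says and that no separate copy of the allocation list is meant to serve the review.

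**What to change.** Sections G, L, N and P need to be reconciled:
- **Section G:** amend the sentence on the box so that the allocation of patients with infections or other serious adverse events, and the number treated per arm, can be released to the IRB. Staff who take no part in outcome collection would release it. Patients, surgeons, the investigator and assessors stay blinded.
- **Section L:** state that the safety review is by arm through that route.
- **Section N:** state how this information feeds the discretion already given to the investigating personnel and the IRB.
- **Section P:** align the restriction of data access to the investigators with the release to the IRB.

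No event threshold or stopping rule is proposed; any criterion is for the investigator and the IRB.

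The cost is a short amendment and a simple allocation log kept by staff who already know the arm, since the existing records are in the box. The IRB would learn the arm of a few patients. No extra visits or patients are needed, and the release involves no comparison of pain or healing between arms.

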APPENDIX A

Data Collection Sheet- Demographics

Pt ID #	SEX	AGE	BMI	OC	TTI
001					
002					
003					
004					
005					

Demographic characteristics

- * Age
- * Sex (female/male)
- * Weight (kg)
- * Height
- * Outerbridge Classification (OC)
- * Estimated time from injury to surgery (Time To Intervention TTI)

APPENDIX B

Data Collection Sheet- Subjective

Pt. ID #	VAS ADL	VAS Kneeling	RSQ	IKDC
001				
002				
003				
004				
005				

Return to Sports Questionnaire

- 6months post op

Visual Analog score for ADL

- 14d, 1, 3, 6, 12, 18, 24 months follow up

Visual Analog score for Kneeling:

- 14d, 1,3,6,12,18, 24 months follow up

IKDC subjective knee evaluation form

- 14d, 1,3,6,12,18, 24 months follow up

APPENDIX C

Data Collection Sheet- Objective

Pt. ID #	XR tunnel placement	XR Donor Site Healing	MRI Donor Site Healing	IKDC	Quadriceps Strength	ROM
001						
002						
003						
004						
005						

Radiographic healing

- 3 months – XR assessment of tunnel placement and donor site healing
- 6 months - MRI Assessment of Donor Site Healing

IKDC Knee examination form

- 14d, 1,3,6,12,18 and 24 months follow up

ROM Measurements

- 14d, 1,3,6,12,18 and 24 months follow up

Quadriceps Strength

- Dynamometry scale

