 - Objective clinical assessments will include IKDC knee examination form scores, ROM measured with goniometer, and quadriceps strength. This data will be collected by an independent researcher (RR, SS) also blinded to treatment. In order to protect the blinding of the study, the senior surgeon(s) (SJN or BB) will examine the patients post operatively but their assessments will not be included in the clinical data collection.

Data Collection Sheet- Objective

Pt. ID #	XR tunnel placement	XR Donor Site Healing	MRI Donor Site Healing	IKDC	Quadriceps Strength	ROM
001						
002						
003						
004						
005						

IKDC Objective Knee Evaluation Form

2000 IKDC KNEE EXAMINATION FORM								
Patient Name: _____		Date of Birth: ____/____/____ <small>Day Month Year</small>						
Gender: F M	Age: _____	Date of Examination: ____/____/____ <small>Day Month Year</small>						
Generalized Laxity:	tight	normal	lax					
Alignment:	obvious varus	normal	obvious valgus					
Patella Position:	obvious baja	normal	obvious alta					
Patella Subluxation/Dislocation:	centered	subluxable	subluxed	dislocated				
Range of Motion (Ext/Flex):	Index Side: passive ____/____/____	active ____/____/____	Opposite Side: passive ____/____/____ active ____/____/____					
SEVEN GROUPS	FOUR GRADES				*Group Grade			
	A Normal	B Nearly Normal	C Abnormal	D Severely Abnormal	A	B	C	D
1. Effusion	None	Mild	Moderate	Severe				
2. Passive Motion Deficit								
ΔLack of extension	<3°	3 to 5°	6 to 10°	>10°				
ΔLack of flexion	0 to 5°	6 to 15°	16 to 25°	>25°				
3. Ligament Examination (manual, instrumented, x-ray)								
ΔLachman (25° flex) (134N)	-1 to 2mm	3 to 5mm(1 ⁺) <-1 to -3	6 to 10mm(2 ⁺) <-3 stiff	>10mm(3 ⁺)				
ΔLachman (25° flex) manual max Anterior endpoint:	-1 to 2mm firm	3 to 5mm	6 to 10mm soft	>10mm				
ΔTotal AP Translation (25° flex)	0 to 2mm	3 to 5mm	6 to 10mm	>10mm				
ΔTotal AP Translation (70° flex)	0 to 2mm	3 to 5mm	6 to 10mm	>10mm				
ΔPosterior Drawer Test (70° flex)	0 to 2mm	3 to 5mm	6 to 10mm	>10mm				
ΔMed Joint Opening (20° flex/valgus rot)	0 to 2mm	3 to 5mm	6 to 10mm	>10mm				
ΔLat Joint Opening (20° flex/varus rot)	0 to 2mm	3 to 5mm	6 to 10mm	>10mm				
ΔExternal Rotation Test (30° flex prone)	<5°	6 to 10°	11 to 19°	>20°				
ΔExternal Rotation Test (90° flex prone)	<5°	6 to 10°	11 to 19°	>20°				
ΔPivot Shift	equal	+glide	++(clunk)	+++ (gross)				
ΔReverse Pivot Shift	equal	glide	gross	marked				
4. Compartment Findings			crepitation with					

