The secondary outcome measures are objective and include radiographic evidence of graft site healing and clinical objective measurements. The primary and secondary outcomes measures for the two groups will be statistically analyzed to evaluate for any differences between the two groups over time using mixed model analysis of variance with Group (PRP vs. no PRP) and the between subjects factor and Time (14d, 1,3,6,12,18 and 24 months post op) as the within subjects factor. Bonferroni corrections will be used for between group or between time pair-wise planned comparisons.

The de-identified data will be entered into an Excel spreadsheet and maintained on a password-protected computer. Once data collection is complete, the principal investigator (SJN) and/or his research assistant (MM) will destroy the master hard copy of identifier codes. Confidentiality of data, data integrity, review of data and study quality will be monitored by the principal investigator and/or his research assistant. Baseline data, demographic data, primary and secondary outcomes will be analyzed using summary statistics, standard deviations and 95% confidence intervals for quantitative data. Qualitative data will be assessed using frequencies and percentages.

J. Informed Consent:

Informed valid written consent will be obtained from all patients at the time of enrollment. This will be in accordance to IRB consent forms

K. Potential Risks & Discomforts:

- a. *Platelet Rich Plasma:* Since PRP is a formulation created entirely from the participants own blood, the complications and risks are extremely low. The anesthesiologist who prepares the blood is highly skilled and will carefully sterilize the skin prior to obtaining the sample. Another side effect that is common is an initial increase in pain and inflammation at the site where the PRP is injected. This occurs because the platelets and blood sample contain natural chemicals that stimulate the immune system. This type of complication is short lived and when it does occur, is treated effectively with pain medication and anti-inflammatory medications, such as Ibuprofen. PRP is not recommended for individuals who have a known bleeding disorder (bleed easily) or are on a medication known to thin the blood such as Coumadin or Lovenox. This makes sense because these patients are more likely to bleed than an individual who has normal bleeding characteristics.

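### Quadriceps strength has no opposite-leg or pre-operative reference, no listed visits and no covariates in its analysis, which gives away precision that is cheap to recover

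*Combined protocol and SAP*

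**What the plan says.** Section F introduces the measure in one sentence: "Objective clinical assessments will include IKDC knee examination form scores, ROM measured with goniometer, and quadriceps strength". ROM has its instrument named there; strength does not. Appendix C adds only "Dynamometry scale" for strength. The IKDC examination and ROM entries just above it each carry a schedule, "14d, 1,3,6,12,18 and 24 months follow up", and strength has none. The pre-operative objective data in section F are time from injury to surgery and a radiographic osteoarthritis grade, so no pre-operative strength reading is planned.

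Section I classes strength as secondary: "The secondary outcome measures are objective and include radiographic evidence of graft site healing and clinical objective measurements". Primary and secondary outcomes go into a mixed-model analysis of variance with Group as the between-subject factor and "Time (14d, 1,3,6,12,18 and 24 months post op) as the within subjects factor". No covariates are named. Bonferroni-corrected pairwise comparisons between groups or times are planned.

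Two other features matter. The IKDC examination form already uses the opposite leg as a reference: it records motion on both sides and grades "One Leg Hop (% of opposite side"). Appendix A collects "Sex (female/male"), weight and height, but section I does not use them.

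**The concern.** A dynamometer reading from the operated leg reflects two things: how strong the patient is in general, and how much strength that leg has lost. Only the second bears on donor-site morbidity. In a sample of both sexes and varied body size, the first can contribute a good deal of variance. The usual ways to remove it are the opposite leg, a pre-treatment value, or baseline covariates. The plan provides neither of the first two for strength and does not use the third.

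The missing visit list adds a second problem. Section I assumes seven time points for the secondary outcomes, while Appendix C gives strength none. An analyst cannot tell which Time levels apply to this outcome.

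At stake is the precision of one secondary comparison. An opposite-leg reading that is not taken at the visit cannot be recovered later.

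**Working it through.** **Plan's own figure.** The only sample-size calculation concerns kneeling pain on a VAS: difference 2.0, SD 3.0, alpha 0.05, power 80%. Taking alpha as two-sided (one-sided would need 28 per group):

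n = 2 × (1.96 + 0.8416)² × 3.0² / 2.0² = 35.3 per group

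This rounds up to 36 against the stated 35; power at 35 is 79.6% (78.5% by the t-test). Allowing for 30% loss, 35 / 0.70 = 50 per group, as stated. The figure reproduces, but no such calculation exists for strength. I take 35 per group from it as the evaluable number.

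**What the design can detect for strength.** For a single-visit comparison at 80% power (normal approximation):

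(1.96 + 0.8416) × √(2/35) = 0.67 SD

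**Gain from the opposite leg as a covariate.** If index-leg and opposite-leg strength correlate r, adjustment multiplies the residual variance by (1 − r²). An effect of 0.5 SD becomes d = 0.5 / √(1 − r²). Power comes from the noncentral t distribution with noncentrality d × √(35/2), 68 degrees of freedom and two-sided alpha 0.05. Both the 0.5 SD effect and every r are assumptions.

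| r | Variance removed | d | Power |
|---|---|---|---|
| 0 (unadjusted) | 0% | 0.500 | 54.1% |
| 0.3 | 9% | 0.524 | 58.0% |
| 0.5 | 25% | 0.577 | 66.3% |
| 0.6 | 36% | 0.625 | 73.2% |
| 0.7 | 51% remains, 49% removed | 0.700 | 82.3% |
| 0.8 | 64% | 0.833 | 93.0% |

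Spending one degree of freedom on the covariate changes each figure by less than 0.1 percentage point.

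**Dependence on the assumed SD.** Take instead an assumed effect of 10% of mean strength, 35 per group, normal approximation. Unadjusted power is 80% if the SD is 15% of the mean, 55% at 20%, 29% at 30% and 18% at 40%. The documents do not say where in this range the trial lies.

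**Covariate or ratio.** With a raw SD of 35% of the mean (assumed), an index/opposite ratio has SD of about √(2 × 0.35² × (1 − r)). At r = 0.3 that is 41%, worse than the raw value; at r = 0.5 it is 35%, no better. Covariate adjustment gives 35% × √(1 − r²), which is 33.4% at r = 0.3 and 30.3% at r = 0.5. The covariate helps at any positive r; the ratio helps only above about 0.5.

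**Where the variation enters the planned model.** Stable differences between patients cancel in within-patient contrasts over time, and so in Group-by-Time. They do not cancel in the overall Group effect or in a between-group comparison at a given visit. The first planned time point is day 14, after treatment, so there is no pre-treatment strength value to anchor change.

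**The case against.** A reader might infer that strength is recorded as one raw value per patient. The documents do not support that. The data sheets are short templates that also give one column each to VAS, IKDC and ROM, which are collected at seven visits. Section I does not say how strength is scaled, and it applies the seven-visit Time factor to the secondary outcomes. The gap is an unlisted schedule and an unspecified limb reference, not a demonstrated one-off measurement.

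A reader might also infer that body size and sex swamp any PRP effect, or that a real difference is likely to be missed. Neither can be shown without a strength SD and effect, and the illustration itself gives slightly better than even power unadjusted. Nor is there systematic bias: "Patients will be randomized using a computer generated randomization table (simple randomization) into one of two treatment arms". Chance imbalance remains possible, but differences between patients are noise.

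The calculation is a single-visit comparison, whereas the plan is a repeated-measures model in which Group-by-Time removes stable differences. That is correct for the interaction. It does not help an effect present at every visit, or the per-visit comparisons.

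Sex, height and weight are already collected and need no new measurement. That stands, and they belong in the model, but section I does not name them, so adding them after the data are seen would be post hoc.

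The strongest technical point is that same-visit opposite-leg strength is measured after randomisation. If treatment alters pain and activity, it could alter the opposite leg as well, and adjusting for it could distort the estimate. The risk is probably small, but it has to be stated and handled.

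**Conclusion.** The point holds as a cheap improvement to a secondary outcome. Strength lacks a limb reference, a pre-operative value, listed visits and covariates, so variation between patients stays in the Group effect and the per-visit comparisons. The consequence is lost precision, not bias. The primary outcome and its sample size are unaffected.

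The gain is modest if the legs correlate weakly (about 4 percentage points of power at r = 0.3) and large if they correlate strongly (about 39 points at r = 0.8). It rests on an assumed 0.5 SD effect, assumed correlations, 35 evaluable patients per group and a single-visit comparison. These figures show direction and plausible scale; they do not estimate this trial's power.

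**What to change.** - **Section F and Appendix C:** record dynamometry for both legs with the same device and blinded examiner, and state the unit. List the strength visits. If feasible, take an opposite-leg reading at the existing pre-operative visit.
- **Section I:** limit the Time factor for strength to the listed visits. Pre-specify analysis of index-leg strength adjusted for opposite-leg strength, plus sex, height and weight. Use the pre-operative opposite-leg reading if it is taken, otherwise the same-visit one. Show index/opposite percent descriptively only.
- **Sensitivity analysis:** if the same-visit reading is used, repeat the analysis adjusting for sex, height and weight alone.

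The cost is an extra column and a few minutes per visit. The post-randomisation covariate is the one statistical drawback, and the sensitivity analysis would show whether the conclusion depends on it.
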